11.7. Withdrawal Due to an Adverse Event

Any subject who experiences an adverse event may be withdrawn from study drug at any time at the discretion of the investigator. If a subject is withdrawn wholly or in part because of an adverse event, both the adverse events page and termination page of the CRF will be completed at that time. The subject will be monitored until the event has resolved or stabilized, until a determination of a cause unrelated to the study drug or study procedure is made, or until the subject is referred to the care of a local health care professional. The investigator must inform the medical monitor as soon as possible of all subjects who are being considered for withdrawal due to adverse events. Additional reports must be provided when requested.

12. STATISTICS

Statistical Analysis of Efficacy

Descriptive statistics will be used to summarize the data for this study. The focus of the analyses will be the evaluation of the relationship between lesion outcomes and subject satisfaction scores from each of the subject satisfaction scales. Because satisfaction is assessed on a subject level and not for each individual lesion, it will be necessary to first summarize multiple lesion outcomes into one score for each subject visit. The analyses will then be implemented at each applicable visit by calculating separate Pearson correlations coefficients between (1) mean change from baseline in per-subject averaged PLA scores across all lesions, and (2) each subject satisfaction scale score at the visit. As a sensitivity analysis, the above statistics will also be calculated using Spearman's rank-order correlation. Exploratory analyses similar to the above will also be conducted between (1) per-subject averaged percent of treated lesions clear (PLA = 0) and (2) each subject satisfaction scale score. A similar exploratory analysis will also be conducted using per-subject averaged percent of lesions clear or near-clear (PLA < 2). Additional multiple regression models may be used across groups of subject satisfaction scales, depending on the pattern of individual subject satisfaction scale outcomes.

Statistical Analysis of Safety Data

Descriptive statistics will be calculated on the safety parameters using the ITT population. The proportion of subjects with adverse events related to study medication will be tabulated and presented by treatment and Medical Dictionary for Regulatory Activities (MedDRA) System Organ Class. Vital signs, and clinically relevant abnormal laboratory results will also be tabulated and presented. No inferential testing will be performed.

Safety summaries will include listings of adverse events incidences within each MedDRA System Organ Class, and changes from pre-application values in vital signs. Adverse event summaries will be presented showing the proportion of subjects experiencing adverse events, both overall and by MedDRA System Organ Class.

Interim Analysis

An interim Analysis will not be conducted for this study.

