- Visit 4 (Day 8) Follow-up Visit
- Visit 5 (Day 15) Study Medication Treatment (if PLA \geq 1)
- Visit 6 (Day 22) Follow-up Visit
- Visit 7 (Day 29) Study Medication Treatment (if PLA \geq 1)
- Visit 8 (Day 36) Follow-up Visit
- Visit 9 (Day 57) Follow-up Visit
- Visit 10 (Day 85) Follow-up Visit
- Visit 11 (Day 113) Follow-up Visit; End of Study

Reference therapy, dosage and mode of administration:

Study drug medication will be applied to 3 target SKs and up to 4 non-target SKs during Visit 2, and for SKs that meet the criteria for retreatment, again on Day 15 (Visit 5) and Day 29 (Visit 7).

Each SK must be treated by a study trained healthcare provider at the site.

Study medication must be applied to each target and non-target SK for approximately 20 seconds. Each target and non-target SK may be treated up to 4 times with approximately 60 seconds between each application.

Criteria for evaluation:

Primary:

- Subject satisfaction after treatment with A-101 (Hydrogen Peroxide) topical solution, 40% (w/w) at Day 85 and Day 113.

Secondary:

- Effectiveness of treatment as measured by the PLA at Day 85 and Day 113.
- Comparison of the PLA score(s) to treatment satisfaction at Day 85 and Day 113.

Statistical methods:

Efficacy Analysis:

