5. TRIAL OBJECTIVES AND PURPOSE

The rationale of this study is to understand a subject's experience and satisfaction after treatment with A-101 40% and how that correlates with a healthcare provider's assessment based on PLA score.

Aclaris Therapeutics, Inc. recently completed three phase III clinical studies (301, 302, and 303) that demonstrated the safety and efficacy of A-101 40% in treating Seborrheic Keratoses.

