⁴Vital signs [including temperature, pulse, respiratory rate, blood pressure, height and weight (Visit 1 only)] will be measured by a qualified staff member at Visit 1, Visit 2, Visit 5, Visit 7, Visit 10, and Visit 11.

⁵Prior medications/therapies will be collected for a time-period of 13 days prior to Visit 1. Refer to Section 8.4 for a list of permitted and restricted concomitant medications.

⁶The treating investigator will identify 3 target SKs and up to 4 non-target SKs. Two (2) target SKs must be on the face, and the additional 1 target SK must be on the neck or décolletage. The 4 non-target SKs may be located on the face, neck, or décolletage.

⁷The investigator will use the Physician's Lesion Assessment (PLA) to assess the severity of each target and non-target SKs at Visits 1, 2, 3, 4, 5, 7, 10, and 11. At Visit 2, Visit 5 and Visit 7, the investigator must assess each target and non-target SK prior to application of the study medication. In order to be eligible for enrollment to the study during Visit 2, the subject must have a PLA grade ≥ 2 for each target and non-target SK.

⁸The investigator will measure the dimensions of each target and non-target SK at Visits 1, 2, 3, 4, 5, 7, 10 and 11. At Visit 2, Visit 5 and Visit 7, the investigator must measure each target and non-target SK prior to application of the study medication. In order to be eligible for enrollment to the study during Visits 1 and 2, each target SK must have a diameter that is between ≥ 5 and ≤ 15 mm (inclusive) and be raised. In order to be eligible for enrollment to the study during Visits 1 and 2, each non-target SK must be a raised SK. At Visits 3, 4, 5, 7, and 10 the investigator must assess the thickness of each target and non-target SK above the surrounding skin. Additional target and non-target SK requirements are outlined in Section 10.1 .

⁹Each target and non-target SK will be photographed at all study visits using the Aclaris Therapeutics, Inc. supplied photography equipment.

¹⁰During Visit 2 each target and non-target SK will be photographed prior to the application of A-101 40%, 10 minutes post application (+2 minutes), and 1-hour post application (± 10 minutes). During Visit 5 and Visit 7, the target and non-target SKs will be photographed prior to the application of A-101 40%, if applicable.

¹¹During Visit 3 each target and non-target SK will be photographed 24-hours post application during Visit 2 (± 2 hours).

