2.	After your experience with A-101 40%, how likely will you pursue future treatment for other SKs on your face or body?  1 – Very unlikely  2 – Unlikely  3 – Neither unlikely or likely  4 – Likely  5 – Very likely
3.	On a scale of 1 – 5, rate your level of satisfaction of your treatment experience with 1 being not satisfied at all and 5 being completely satisfied?  1 – Not satisfied at all  2 – Slightly satisfied  3 – Moderately satisfied  4 – Satisfied  5 – Very satisfied
4.	On a scale of 1 – 5, rate your level of satisfaction with the appearance of your skin treated with A-101 40% with 1 being not satisfied at all and 5 being completely satisfied?  1 – Not satisfied at all  2 – Slightly satisfied  3 – Moderately satisfied  4 – Satisfied  5 – Very satisfied
5.	What is the likelihood you will get other SKs treated in the future with A-101 40%?  1 – Not likely at all  2 – Slightly likely  3 – Moderately likely  4 – Very likely  5 – Extremely likely
6.	What is the likelihood you will recommend A-101 40% to a friend/relative?  1 – Not likely at all  2 – Slightly likely  3 – Moderately likely  4 – Very likely  5 – Extremely likely

7.	
For an SK you would like to treat in the future, please rank your preferred treatment method (1 – most preferred; 5 – least preferred).
 
 A-101 40% (topical application)
 
 Cryotherapy (freezing with 196 °C liquid nitrogen)
 
 Curettage (scraping off tissue with a sharp instrument)
 
 Electrodesiccation (burning off with high-voltage electricity)
 
 Other (please describe)

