8.	
After treatment with A-101 40%, how bothered are you by the appearance of your treated SKs today?
 
 1 – Not bothered at all
 
 2 – A little bit bothered
 
 3 – Neutral
 
 4 – Somewhat bothered
 
 5 – Extremely bothered

9.	
Since your treatment with A-101 40%, how do you feel about getting your untreated SKs treated in the future?
 
 Anxious/Nervous
 
 Concerned/Worried
 
 Unsure/Neutral
 
 Hopeful
 
 Excited

10.	
Please indicate the level of agreement you have to the following statements:
 
A) Since my treatment with A-101 40%, I feel more confident:
 
 Strongly disagree
 
 Disagree
 
 Neither disagree or agree
 
 Agree
 
 Strongly agree
 
B) Since my treatment with A-101 40%, I feel more attractive:
 
 Strongly disagree
 
 Disagree
 
 Neither disagree or agree
 
 Agree
 
 Strongly agree
 
C) Since my treatment with A-101 40%, I feel less embarrassed:
 
 Strongly disagree
 
 Disagree
 
 Neither disagree or agree
 
 Agree
 
 Strongly agree
 
D) Since my treatment with A-101 40%, I feel more comfortable being photographed in pictures:
 
 Strongly disagree
 
 Disagree
 
 Neither disagree or agree
 
 Agree
 
 Strongly agree

Subject initials: _____

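### Does correlating satisfaction with raw change in mean PLA, without baseline adjustment, distort the PLA-satisfaction relationship?

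*Protocol*

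**What the plan says.** Protocol section 12, repeated in the synopsis, first reduces each subject's lesions to one score per visit. It then takes a Pearson correlation between each satisfaction scale and the "mean change from baseline in per-subject averaged PLA scores across all lesions". Spearman's correlation on the same score is the sensitivity analysis. Two exploratory correlations follow, one with the percent of treated lesions that are clear (PLA 0) and one with the "per-subject averaged percent of lesions clear or near-clear (PLA < 2)". Further regression models are allowed across groups of satisfaction scales, but no baseline covariate is named.

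At enrolment "the subject must have a PLA grade ≥ 2 for each target and non-target SK" (Protocol Table 3, footnote 7), and the scale ends at 3, so baseline is 2 or 3 for every lesion. The synopsis lists as a secondary criterion the "Comparison of the PLA score(s) to treatment satisfaction at Day 85 and Day 113". Protocol section 5 speaks of a healthcare provider's "assessment based on PLA score".

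The end-of-study form in Appendix 3 has ten graded items:
- Items 4 and 8 concern present appearance: "appearance of your skin" and "how bothered are you by the appearance of your treated SKs today".
- Items 10A to 10D are worded as change, for example "Since my treatment with A-101 40%, I feel more confident".
- Items 2, 3, 5 and 6 concern the treatment experience, future treatment or recommendation.

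SAP section 3 covers PLA and safety only. It leaves the satisfaction analysis and its relation to PLA to a separate plan, which is not among the documents.

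**The concern.** A change score contains baseline by construction. Two fully cleared subjects can score -2 and -3 only because one started with thin lesions and the other with thick ones. A subject who goes from 2 to 0 ties with one who goes from 3 to 1 and still has visible lesions. Spearman on the same score removes neither effect.

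The rationale and the secondary criterion name the PLA score, while section 12 leads with its change and does not say whether end state or improvement is meant. If subjects judge how they look now, baseline thickness is noise in the lesion score and pulls r towards zero. Differences in r between items could then reflect the score chosen as well as the subjects' views. Section 12 calls this relationship the focus of the analyses, so the point estimates will be read.

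**Working it through.** The plan states no expected r and no sample-size rationale, so there is no figure to reproduce. The checks below cover the size of the dilution, what the plan already does about it, and whether baseline adjustment would do better.

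**Inputs.** From the documents: n = 30, 3 to 7 lesions per subject, baseline PLA 2 or 3, final PLA 0 to 3. Assumed, because the documents give none: the SDs of subject-mean baseline (B) and final (F) PLA, their correlation rho, and the correlation r of satisfaction with final PLA.

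**1. Dilution if satisfaction depends on final PLA only.** With C = F - B and k = SD(B)/SD(F),

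r(S,C) = r(S,F) × corr(F,C), where corr(F,C) = (1 - rho·k) / √(1 + k² - 2·rho·k).

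A lesion-level simulation over 324 assumed scenarios gave k of 0.29 to 0.70 (median 0.45) and corr(F,C) of 0.78 to 0.96 (median 0.90). An r of 0.50 would therefore be seen as about 0.45 (0.39 to 0.48). The dilution is real and modest.

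**2. What the plan already covers.** On a 0 to 3 scale, with proportions of a subject's lesions,

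mean PLA = (1 - clear) + (1 - clear or near-clear) + thick.

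The two exploratory measures therefore carry everything in mean visit PLA except the thin/thick split among uncleared lesions. In the 324 scenarios their correlations with final mean PLA were 0.85 to 0.96 in absolute value. They also deal with the worrying cases:

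| Course (all lesions) | Change | Percent clear | Percent clear or near-clear |
|---|---|---|---|
| 2 to 0 | -2 | 100 | 100 |
| 3 to 0 | -3 | 100 | 100 |
| 3 to 1 | -2 | 0 | 100 |

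Percent clear puts the two cleared subjects together and separates the third.

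**3. Would adjustment for baseline do better?** For Pearson, the partial correlation given B is the same whether F or C is used. If satisfaction depends on F only,

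partial r = r·√(1 - rho²) / √(1 - r²·rho²).

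This never exceeds r itself, and it falls as rho rises. With r = 0.60 and k = 0.45:

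| rho | corr(F,C) | raw change, 0.60 × corr(F,C) | partial r |
|---|---|---|---|
| 0.2 | 0.91/√1.0225 = 0.900 | 0.540 | 0.588/√0.9856 = 0.592 |
| 0.5 | 0.775/√0.7525 = 0.893 | 0.536 | 0.520/√0.9100 = 0.545 |
| 0.6 | 0.73/√0.6625 = 0.897 | 0.538 | 0.480/√0.8704 = 0.514 |
| 0.7 | 0.685/√0.5725 = 0.905 | 0.543 | 0.428/√0.8236 = 0.472 |

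Setting the two formulas equal with r = 0.54, the partial r drops below raw change once rho passes about 0.35 (k = 0.3) to 0.66 (k = 0.6). A lesion-level simulation with r = 0.6 agreed. When thick lesions respond much worse (rho 0.58 to 0.67), raw change gave 0.525 to 0.544 and the partial r 0.485 to 0.519. With weaker dependence the partial r was higher.

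If satisfaction depends on C only, the same formula applies with corr(B,C) in place of rho. The partial r can then only equal or fall below raw change. The simulated loss was 0.00 to 0.04.

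**4. Gain over what is planned.** In a separate simulation (latent r 0.6, end state drives), raw change gave 0.50 to 0.52, percent clear 0.51 to 0.52, percent clear or near-clear 0.54 to 0.55, and the partial r 0.54 to 0.58. Over those scenarios and the matching ones with latent r 0.4, raw change fell 0.01 to 0.08 below the partial r. When satisfaction mixed end state and improvement, the gap was 0.002 to 0.016.

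**5. Precision.** By Fisher z, atanh(0.50) = 0.549 and 1.96/√27 = 0.377. The limits are tanh(0.172) = 0.17 and tanh(0.926) = 0.73.

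**The case for a change.** The strongest case for the concern is that the distortion is structural and cheap to address: one or two sentences, using baseline PLA that is already collected. The two end-state measures are exploratory and dichotomise a four-grade scale. Percent clear did no better than raw change in the simulation, and percent clear or near-clear still ties 2-to-0 with 3-to-1. SAP section 3.7 summarises PLA as an end state with no change from baseline, so the lead correlation uses a different construct without explanation. A small effect relative to the interval is still a bias, and in a descriptive report the point estimates are what people read.

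The algebra stands: raw change contains baseline, and it loses a little if end state alone drives satisfaction. The rest does not make an error. The wording about PLA scores does not exclude change. If one lesion score cannot suit ten items of mixed wording, one partial correlation applied to all of them cannot either. Labelling each item as end state or improvement would not alter that Pearson statistic, which is identical for both scores. Its cost is also larger than one degree of freedom, because it can fall below raw change even when end state drives satisfaction. How each item is treated belongs in the separate satisfaction plan, so the protocol's silence does not show that it was left out.

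**Conclusion.** The concern does not hold as an error. Change from baseline is a defensible lead summary, it suits items 10A to 10D, and section 12 pairs it with two correlations free of baseline. If end state alone drives satisfaction, r is multiplied by about 0.90 (0.78 to 0.96 over the assumed scenarios). If improvement drives it, there is no such loss and baseline adjustment can only equal raw change or do worse. Whether adjustment helps in the end-state case depends on the baseline-final correlation, which the documents do not give, so the choice is a trade-off.

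A conditional shift of about 0.01 to 0.08 in a descriptive correlation, with a 95% interval of 0.17 to 0.73 at r = 0.50 and no threshold attached, changes no conclusion of the trial. These sizes rest on assumed SDs and correlations. Their only anchor in the documents is the 28.2% mean clearance of target lesions in Study 303, a per-protocol Day 148 figure from a study of face, trunk and extremities. The finding that adjustment is not reliably better comes from the formulas and does not depend on that figure.

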¹²A-101 40% will be applied to each target and non-target SK by a study trained healthcare provider at the site. Each target and non-target SK will be treated with A-101 40% following confirmation of subject eligibility and study enrollment at Visit 2. If a target or non-target SK meets the criteria for retreatment as defined in Section 9.5, the SK will be retreated at Visit 5 and Visit 7. Following application of A-101 40%, subjects must NOT wash/submerge a target and non-target SK for at least 6 hours and they must NOT apply any topical products to any target or non-target SK for at least 6 hours.

¹³Subjects will be asked to assess how satisfied they are with the treatment experience they received for the target and non-target SKs at the specified visits. On Visit 2 the subject will complete the assessment prior to application of A-101 40%. On Visit 3 the subjects will complete the assessment approximately 24 hours after the treatment. On Visit 6 and Visit 8 the subjects will complete the assessment approximately 1 week after the treatment, only if the subject received treatment on Visit 5 or Visit 7. The subject will complete the assessment during the Visit 10 and Visit 11.

¹⁴All concomitant therapies including (topical and oral) prescription medications, over the counter medications, natural supplements and non-drug therapies including chiropractic, physical therapy, and energy-based therapy must be documented in the subject CRF. Subjects must not apply any topical products (*e.g.*, moisturizers, sunscreen, etc.) to their target and non-target SKs within 12 hours prior to any study visit.

¹⁵The reporting period for SAEs begins when the subject signs the informed consent form. Refer to Section 11.6 for instructions on the reporting of SAEs. Non-serious clinical adverse events will be collected following the application of the study medication at Visit 2 and continue through Visit 11. All safety reporting (AEs and SAEs) will conclude at Visit 11.

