APPENDIX 3.

A-101-SEBK-402 Pre-Dose Subject Satisfaction Assessment for Treatment Experience (complete at Day 1/Visit 2 prior to treatment)	
Subject Number: _____	
Date: _____ Time: _____	
1. a.	What prior treatments have you used/had performed for SK removal? (Select all that apply)  Cryotherapy (freezing with liquid nitrogen)  Curettage (scraping off tissue)  Electrodesiccation (burning off with electricity)  Laser therapy (burning off)  Other (provide name) _____
2.	How bothered are you by the appearance of your face/hairline/neck SKs?  1 – Not bothered at all  2 – A little bit bothered  3 – Neutral  4 – Somewhat bothered  5 – Extremely bothered
3.	How do you feel about getting your SKs treated? (Select all that apply)  Anxious/Nervous  Concerned/Worried  Unsure/Neutral  Hopeful  Excited
4.	What prior facial cosmetic treatment(s), excluding cryotherapy for SK removal, have you had for your face in a dermatology clinic or MedSpa? (Select all that apply)  Botox injections  Hyaluronic acid fillers (e. g., Juvederm, Restylane, etc.)  Hair removal with laser or pulsed light  Chemical peel  Microdermabrasion  Plastic surgery  Other (provide name) _____  None, A-101 40% will be my first cosmetic treatment for my face at a medical clinic

Subject initials: _____

A-101-SEBK-402 End of Study Subject Satisfaction Assessment for Treatment Experience (complete at Day 85/Visit 10 and Day 113/Visit 11)	
Subject Number: _____	
Date: _____ Time: _____	
1.	Please check prior treatments you have personally had for SKs (check mark all that apply).  Cryotherapy (freezing with 196 °C liquid nitrogen)  Curettage (scraping off tissue with a sharp instrument)  Electrodesiccation (burning off with high-voltage electricity)  Other (please describe)

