### **1.2 SAMPLE SIZE**

A total of 30 subjects are planned to enroll in the study.

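### Protocol Section 12 relates PLA change to the raw Day 85/113 bother score and specifies no use of the pre-dose bother score; a baseline-adjusted correlation should be added beside it.

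*Protocol*

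**What the plan says.** Protocol Section 12 (repeated in the Synopsis) makes the relation between lesion outcomes and satisfaction scores the focus of the analysis. It does so by "calculating separate Pearson correlations coefficients between" two quantities: "1) mean change from baseline in per-subject averaged PLA scores across all lesions", and "2) each subject satisfaction scale score at the visit". Spearman's coefficient is the sensitivity analysis. Exploratory versions put the percentage of lesions clear, or clear or near-clear, in place of PLA change. None of these is adjusted for anything. The only multivariable provision is optional and names no baseline term: "Additional multiple regression models may be used across groups of subject satisfaction scales".

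Appendix 3 holds two bother items. Pre-Dose item 2, completed at Visit 2 before application (Table 3, footnote 13), asks "How bothered are you by the appearance of your face/hairline/neck SKs". End of Study item 8, completed at Visits 10 and 11, asks "how bothered are you by the appearance of your treated SKs today". The five response options are identical, running from 1 (no bother) to 5 (extreme bother). The stems differ in the lesions they cover.

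The SAP supplied covers PLA and safety only. Its Section 3 leaves the satisfaction scores and their relation to PLA to a separate plan. On sample size, SAP Section 1.2 says only this: "A total of 30 subjects are planned to enroll in the study".

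**The concern.** A raw score at Day 85 mixes what treatment changed with how bothered the subject was to begin with. A subject who scored 1 before treatment and 1 afterwards counts as a better outcome than one who moved from 5 to 2, although only the second improved.

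This can affect the estimated association in two ways. If pre-dose bother predicts later bother but is unrelated to PLA improvement, it adds variation to the later score and pulls the coefficient toward zero. If it is also related to PLA improvement, it shifts the coefficient further, in a direction that depends on the sign of that link. A positive link is conceivable: every lesion enters at PLA 2 or 3 (Protocol Section 10.1.2), a grade 3 lesion has more room to fall, and subjects with thicker lesions may start more bothered. That last step is an assumption. What is at stake is how well the study describes the link between lesion improvement and bother, one part of the stated rationale in Protocol Section 5.

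**Working it through.** **The plan's own figure.** There is none to reproduce. The documents give N = 30 with no expected correlation, alpha or power.

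**Inputs.** From the documents: n = 30; PLA as change from baseline; bother as the raw visit score; a pre-dose bother score on the same 1 to 5 anchors. Assumed, because the documents are silent:
- p, the correlation of PLA improvement with later bother after adjustment for pre-dose bother: -0.50. Improvement is taken as positive, so a negative value means that better lesions go with less bother.
- rho, the correlation of pre-dose with later bother: 0 to 0.7.
- a, the correlation of PLA improvement with pre-dose bother (the link): -0.2, 0 or 0.3.

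**Formula.** Rearranging the definition of a partial correlation, raw r = p × sqrt[(1 - rho²)(1 - a²)] + rho × a.

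**At rho = 0.5:**
- a = 0: -0.50 × sqrt(0.75) = -0.433
- a = 0.3: -0.50 × sqrt(0.75 × 0.91) + 0.15 = -0.413 + 0.15 = -0.263
- a = -0.2: -0.50 × sqrt(0.75 × 0.96) - 0.10 = -0.424 - 0.10 = -0.524

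**Raw correlation over the range, with the adjusted value fixed at -0.50:**

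| rho | a = -0.2 | a = 0 | a = 0.3 |
|---|---|---|---|
| 0 | -0.490 | -0.500 | -0.477 |
| 0.3 | -0.527 | -0.477 | -0.365 |
| 0.5 | -0.524 | -0.433 | -0.263 |
| 0.7 | -0.490 | -0.357 | -0.131 |

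**Check on 1 to 5 scores.** A simulation with n = 30, bother rounded and limited to 1 to 5, and 4,000 replicates per cell gave, at rho = 0.5, mean raw and adjusted values of -0.41 and -0.45 for a = 0, and -0.24 and -0.43 for a = 0.3. Rounding shrinks all the coefficients, but the direction is the same.

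**Precision, for scale.** With Fisher's z, the half-width at n = 30 is 1.96/sqrt(27) = 0.377. An r of 0.50 has a 95% interval of 0.17 to 0.73. A shift from -0.50 to -0.43 is small against that; a shift to -0.26 is not negligible.

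**Covariate or difference.** With equal SDs, the correlation of PLA improvement with change in bother is (raw r - a)/sqrt[2(1 - rho)]. At rho = 0.5 this is -0.433 for a = 0, -0.563 for a = 0.3 and -0.324 for a = -0.2. At rho = 0.2 and a = 0 it is -0.387, weaker than the raw -0.490. A difference therefore does not reliably recover the adjusted value. It would also subtract answers about different sets of lesions: the pre-dose stem omits the décolletage, where the third target SK may lie, while item 8 concerns the treated SKs. A covariate only has to predict the outcome.

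**Cost of adjusting.** If pre-dose bother predicts nothing, the standard error on the z scale goes from 1/sqrt(27) to 1/sqrt(26), a factor of sqrt(27/26) = 1.019, or about 2% wider.

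**The case against.** Several objections stand and limit the point.
- **The analysis is deferred.** SAP Section 3 assigns it to a plan that is not among the documents. A reader might infer that the trial never uses the pre-dose score. The documents show only that Section 12 and the supplied SAP do not specify a use.
- **The raw correlation answers a legitimate question.** Protocol Section 5 asks how experience and satisfaction after treatment correlate with the PLA-based assessment. The unadjusted coefficient answers that; the adjusted one answers a baseline-conditional question. A reader might infer that the planned coefficient is wrong and should be replaced. The documents do not support that.
- **Nothing is tested.** Section 12 describes a descriptive analysis and sets no alpha, hypothesis or power for it. Restating the dilution as lost power would measure something that the plan does not promise.
- **One item is affected.** Item 8 is one of ten rating items on the End of Study form (2 to 6, 8 and 10A to 10D), and Section 12 does not list which items count as satisfaction scales. Satisfaction itself is asked in items 3 and 4, which have no pre-dose counterpart, so the main objective is untouched.
- **The effect may be small.** The differing stems may lower rho. The required recent cryosurgery suggests a treatment-seeking group that may vary little in pre-dose bother (an inference). Baseline mean PLA can span only one grade.

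These objections settle the form of the change, which is to add and not to replace. They do not remove the reason for it: the baseline is already collected, and choosing an adjustment after seeing 30 subjects' data would be open to selective reporting.

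**Conclusion.** The point holds as a cheap improvement to one secondary analysis. As written, Section 12 sets PLA change against the raw later bother score and specifies no use of a baseline collected on the same anchors.

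The size and the direction both depend on two correlations that the documents do not give. For an assumed adjusted value of -0.50, the raw value lies between -0.48 and -0.36 for rho from 0.3 to 0.7 with no link between pre-dose bother and PLA improvement, and between -0.37 and -0.13 with a link of 0.3. With a link of -0.2 it lies between -0.49 and -0.53, so it is little changed or slightly inflated. With rho and the link both zero it does not change. Dilution is therefore possible but not established. Whether the separate satisfaction plan already makes the adjustment could not be checked.

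**What to change.** In Protocol Section 12 and in the separate satisfaction analysis plan, if it does not already do so:
- Keep the unadjusted correlation for End of Study item 8.
- Add a pre-specified partial correlation between change in per-subject mean PLA and item 8 at Day 85 and at Day 113, adjusted for Pre-Dose item 2 (Pearson, with the Spearman version as sensitivity analysis).
- Report a cross-tabulation of pre-dose by later bother at each of the two visits.
- Enter the pre-dose score as a covariate, not as a difference, and give the difference in stems as the reason.

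The cost is a sentence or two in the plan, one extra table and one degree of freedom. All the data are already collected. No power gain should be claimed, since the plan specifies no test.
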